- The SAD part will consist of a single-dose escalation phase in up to 3 cohorts and a food effect cohort.
- Cohorts 1 and 2 will comprise of a 4-way crossover within each cohort. Participants will receive three doses of GSK3494245 and a randomised placebo dose, administered in the fasted state. An optional third cohort may be included to further evaluate safety or PK or to evaluate additional doses.
- Cohort 3 will investigate the effect of food following a single dose. It will comprise of a 4-way crossover in which participants will receive GSK3494245 and placebo in both fasted and fed conditions and in a 1:1 ratio.
- On completion of Cohort 3, Cohort 3a will assess single ascending doses of GSK3494245 taken with food, following the same 4-way crossover design as Cohorts 1 and 2. Participants will receive three doses of GSK3494245 and a randomised placebo dose. An optional cohort may be included to further evaluate safety or PK or to evaluate additional dose levels.
- Up to 8 10 different dose levels will be studied in the SAD part.
- The MAD part will be a twice-daily (BID) 7-day repeat dose design in up to 5 cohorts of participants (Cohorts 4, 5, 6, 7 and 8), with doses administered in the fed state. Based on emerging data, the dosing regimen may be altered to a three-times daily (TID) regimen in fed conditions, with the three doses administered 6 hours apart on each day.. Up to a maximum of 5 dose levels will be studied in the MAD part. CCI [REDACTED]
[REDACTED]

All participants in the study will attend a screening visit within 28 days prior to their first dose and a follow-up visit within 7-14 days after their final dose. If required, additional follow-up visits may be scheduled.

Disclosure Statement: This is a sequential, cross-over (SAD part, within cohort), parallel group (MAD part), interventional study that is participant, investigator and sponsor study team blinded (apart from unblinded team members, prespecified in the protocol).

Number of Participants:

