Procedure	Screening (Up to 28 days before Day 1)	Study Period (Days)										Follow-up (7-14 days post last dose) ¹ / Early Withdrawal ²	Notes
		-1	1	2	3	4	5	6	7	8			
CCI													
Lactate Sampling			X	X			X					Blood sample to assess lactate at the following timepoints: 
- Day 1, 2 and 5: predose and post morning dose at 2hr, 4hr, 8hr, 12hr*, 16hr.- * (prior to evening dose) Assessment timepoints may be modified, as deemed necessary by the Investigator and sponsor.	
Telemetry			←X→					←X→				Continuous at least 48 hr post-morning dose on Day 1 and at least 24 hr post morning dose on Day 6. Initiate at least 15 min. prior to first dose on Day 1 and Day 6 respectively. If a waveform abnormality is detected, then extend for further 24hr	
Randomisation			X										
Study Treatment			X	X	X	X	X	X	X*			BID dosing: GSK3494245 or placebo will be administered using a 12hr dosing interval (morning and evening dosing). TID dosing: GSK3494245 or placebo will be administered using a 6 hr dosing interval (morning, afternoon and evening dosing) *Only single dose on last day of dosing period.	
12-Lead ECG	T	X	T	X	X	X	X	X	X		X	12-Lead ECG to be conducted on Day-1 and pre-dose Day 1 and then at the subsequent time points post first-dose: 30 min, 1 hr, 1.5hr, 2hr, 2.5hr, 4hr, 6hr, 8hr 12hr and 14hr. Day 2 to 7: 12-Lead ECG at pre-morning dose Timings will be reviewed as cohorts progress and may be adjusted to ensure appropriate measurements relative to peak concentrations for	

CONFIDENTIAL

208441
Protocol Amd 6

Procedure	Screening (Up to 28 days before Day 1)	Study Period (Days)									Follow-up (7-14 days post last dose) ¹ / Early Withdrawal ²	Notes
		-1	1	2	3	4	5	6	7	8		
												subsequent cohorts T = assessments done in triplicate, at Pre-dose only . If any abnormal ECG reading is recorded, refer to Section 7.1.5 for appropriate action.

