Vital signs	X	X	T*	X	X	X	X	X	X	X	X	
Vital signs to include HR, BP, temperature and respiration rate. BP and HR will be assessed in a supine position.
 
Vital Signs to be conducted on Day-1 and pre-morning dose Day 1 and then at the subsequent time points post first-dose: 2hr, 4hr, 6hr, 8hr, 12hr and 14hr. Days 2-6: pre-morning dose assessments only. Vitals Signs to be conducted on pre-morning dose Day 7 and then at the subsequent time points post-morning dose; 2hr, 4hr, 6hr, 24hr (Day 8)
 
Timings will be reviewed as cohorts progress and may be adjusted to ensure appropriate measurements relative to peak concentrations for subsequent cohorts T = assessments done in triplicate, *At Pre-dose only (except tympanic temperature and respiration rate)

PK Blood Sampling			<=====X=====>									
PK samples will be collected at the following time points in case of BID administration: Day 1: pre-morning dose, 10min, 30min, 1hr, 1.5hr, 2hr, 2.5hr, 3hr, 4hr, 5hr, 6hr, 8hr, 10hr, and 12hr (12hr taken at pre-dose). Days 4 – 6: Morning pre-dose PK samples collected for each dose Day 7: PK samples will be collected pre- dose and at

CONFIDENTIAL

208441
Protocol Amd 6

Procedure	Screening (Up to 28 days before Day 1)	Study Period (Days)									Follow-up (7-14 days post last dose) ¹ / Early Withdrawal ²	Notes
		-1	1	2	3	4	5	6	7	8		
											
the following time points post dose: 10min, 30min, 1hr, 1.5hr, 2hr, 2.5hr, 3hr, 4hr, 5hr, 6hr, 8hr, 10hr, 12hr and 14hr
 
PK samples will be collected at the following time points in case of TID administration: Day 1: pre-morning dose, 10min, 30min, 1hr, 1.5hr, 2hr, 2.5hr, 3hr, 4hr, 5hr, 6hr (6hr taken at pre-dose). Days 4 – 6: Morning pre-dose PK samples collected for each dose Day 6: PK samples will be collected pre-evening dose and at the following time points post evening-dose: 10min, 30min, 1hr, 1.5hr, 2hr, 2.5h,3hr, 4hr, 5hr and 6hr Day 7: PK samples will be collected pre-dose and at the following time points post dose: 10min, 30min, 1hr, 1.5hr, 2hr, 2.5hr, 3hr, 4hr, 5hr, 6hr, 8hr, 10hr, 12hr and 14hr Only one dose is administered on Day 7 The time points stated may be modified depending on emerging SAD and MAD PK profiles.
 
All samples collected will be 2mL in volume
	

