4.4. Scientific Rationale for Study Design

This study will be the first administration of GSK3494245 in human participants. The primary purpose of the current study is to characterise the safety and tolerability of GSK3494245 in healthy participants within a controlled PK range. The study will additionally seek to understand the secondary and exploratory endpoints. Specific scientific considerations which contribute to the study design include:

- In the SAD part, this study employs a randomised sequential crossover design to allow for dose comparison between and within participants at different dose levels. In addition, this design minimises participant numbers across the SAD part of the study and is appropriate given the short-estimated half-life of GSK3494245 (approximately 4 h), which enables a short washout period.
- Furthermore, a food-effect evaluation is planned to support progression into patient studies. An assessment of food effect on the exposure to GSK3494245 will be incorporated into the SAD part of the study. Preliminary assessment of food-effect hinted a marginal decrease in the drug exposure which could possibly be attributed to high stomach solubility in the fasted acidic stomach that is not present in the fed state due to a higher pH. In the presence of food, the exposure may be slightly lower or the same in terms of overall trend. Please see Section 9 for further details on how sample size was determined for the food effect cohort. The exact sample size for the evaluation of the food effect will be determined based on the variability of the AUC and C_{\max} observed in Cohorts 1 and 2. Up to a maximum of 16 participants will be recruited to allow for 12 evaluable participants, however as few as 10 evaluable participants may be required, in which case the number of participants recruited could be slightly lower. The

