Table 6 list the proposed dose levels for the MAD part of the study, together with exposure predictions (based on current study data from the SAD part up to 160mg) and expected safety cover for the 95th percentile of the population. Dose levels are only illustrative and actual doses might slightly differ once complete PK up to the highest dose in the SAD part of the study is available. However, the starting dose level for MAD will not exceed 30 mg BID or TID. It should be noted that calculated steady state plasma AUC_{24h} exposure on Day 7 will be used as part of PK stopping criteria following repeat dosing. PK sampling on Day 7 at steady state is proposed for 0-12h for BID dosing or 0-6h for TID dosing (in the event that TID schedule is selected). Hence, AUC_{24h} (Day 7) will be derived as $2 \times AUC_{12h}$ or $3 \times AUC_{6h}$ for BID or TID dosing, respectively.

Table 4 **Projected plasma GSK3494245 AUC_{0-∞} and C_{max} (mean and 95th percentile) following single oral doses of GSK3494245 in scenario 1, with Fold Cover to preclinical NOAEL**

Dose (mg)	Predicted Human Plasma Exposures*				Safety Margins with respect to NOAEL [#]			
	AUC _{0-∞} (ng×h/mL)		C _{max} (ng/mL)		AUC _{0-∞} (ng×h/mL)		C _{max} (ng/mL)	
	mean	p95	mean	p95	mean	p95	mean	p95
20 ^s	1209.8	1983.8	130.7	199.8	40.3	24.5	46.7	30.5
60 ^s	3642.1	6033.8	395.9	570.0	13.4	8.1	15.4	10.7
120 ^s	7284.3	12067.6	791.7	1140.1	6.7	4.0	7.7	5.4
200	11968.9	19589.5	1309.4	1964.2	4.1	2.5	4.7	3.1
300	17995.6	28360.9	1938.2	2841.8	2.7	1.7	3.1	2.1
400	23699.1	37665.2	2585	3755	2.1	1.3	2.4	1.6
500	30185.2	49827.2	3193.2	4727.6	1.6	1	1.9	1.3
600	36198.1	58042	3909.9	5640.9	1.3	0.8	1.6	1.1

*The predicted human exposures are in blood and the animal exposures are in plasma. Human Blood to plasma ratio (B/P ratio = 0.88) is used for conversion of predicted blood exposures to obtain human plasma exposures.

[#]NOAEL exposures in female minipig: AUC = 48700 ng×h/mL; C_{max} = 6100 ng/mL. Safety margin = NOAEL exposure parameter value/predicted human plasma exposure parameter.

^sDose not included in simulations, exposure derived proportionally from simulated doses.

Table 5 **Projected plasma GSK3494245 AUC_{0-∞} and C_{max} (mean and 95th percentile following single oral doses of GSK3494245 in scenario 2, with Fold Cover to preclinical NOAEL**

Dose (mg)	Predicted Human Plasma Exposures*				Safety Margins with respect to NOAEL [#]			

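### For TID dosing, 3 x AUC6h from the Day 7 morning dose understates the daily AUC used for PK stopping, by roughly 0-30%, because the dosing intervals are 6-6-12 h.

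*Protocol*

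**What the plan says.** Protocol Section 4.5.3 says that calculated steady-state AUC24h "exposure on Day 7 will be used as part of PK stopping criteria following repeat dosing". On sampling it says "PK sampling on Day 7 at steady state is proposed for 0-12h for BID dosing or 0-6h for TID dosing", and it derives AUC24h as 2 x AUC12h for BID and 3 x AUC6h for TID. Section 7.1.1 sets the MAD limits: AUC24h 48,700 ng*h/mL and Cmax 6,100 ng/mL at steady state, applied to any single participant.

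The TID schedule is described in the Synopsis, "with the three doses administered 6 hours apart on each day", and the Schedule of Activities (Section 1.3.2) names the doses as morning, afternoon and evening. On Day 7, "Only one dose is administered on Day 7".

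The same schedule plans more TID sampling than Section 4.5.3 mentions. Day 7 is sampled to 14 h, and there is a second profile: "Day 6: PK samples will be collected pre-evening dose and at the following time points post evening-dose", running to 6 h. TID accumulation and time-invariance (Section 9.5.2; SAP Sections 7.4 and 7.5) already use that Day 6 evening dose.

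**The concern.** Multiplying one interval's AUC by the number of daily doses gives the 24 h AUC only when the intervals are equal. That is so for BID (12-12 h). For TID they are 6-6-12 h, so 3 x AUC6h covers 18 of the 24 hours. The interval it triples is also the one after the 12 h overnight gap, when least drug is carried over from earlier doses.

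The figure feeds a participant-level exposure stop in a first-in-human study. Section 2.3.1 also lists keeping total daily AUC below the minipig NOAEL as a mitigation for the renal findings. A value that reads low lets true exposure pass the limit before the AUC rule acts.

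**Working it through.** **Inputs.** Section 4.5.1 and Table 3: CL 3.81 (scenario 1) and 6.67 mL/min/kg (scenario 2), V 1.28 L/kg, ka 0.7/h, F 80% and 64%, 70 kg, 30% CV on CL. Section 4.5.3: blood:plasma ratio 0.88, limits 48,700 and 6,100, Table 6. Section 4.4: half-life of about 4 h.

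**Check of the model against the plan's own figures.** The documents give no worked value for 3 x AUC6h, so I reproduced Table 4 first. Scenario 1, 20 mg: CL = 3.81 x 0.06 x 70 = 16.0 L/h. Typical plasma AUC = 0.8 x 20 / 16.0 / 0.88 = 1,136 ng*h/mL. The mean at 30% CV is 1,136 x exp(ln(1.09)/2) = 1,186, against 1,209.8 in Table 4. Scenario 2 gives 542 against 552.8 in Table 5. Both are about 2% low. Typical Cmax is 127.1 against 130.7, and 84.7 against 86.8. The model is adequate.

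**Direction.** Let a1, a2, a3, ... be successive 6 h slices of the single-dose AUC, summing to AUCinf. With doses at 0, 6 and 12 h and none at 18 h:
- AUC24h at steady state = 3 x AUCinf.
- Morning AUC6h = AUCinf - (a2 + a6 + a10 + ...), because the dose that would have come 6 h earlier is missing.
- So 3 x AUC6h / AUC24h = 1 - (a2 + a6 + ...)/AUCinf, which cannot exceed 1 under linear PK.

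For BID, 2 x AUC12h / AUC24h = 1.000.

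**Size under Table 3.** For one compartment, let f(x) = (e^(-6x) - e^(-12x))/(1 - e^(-24x)). The missing share is [ka f(k) - k f(ka)]/(ka - k).
- Scenario 1: k = 0.1786/h, f(k) = 0.2283, f(0.7) = 0.0148. Share = (0.1598 - 0.0026)/0.5214 = 0.301; ratio 0.699.
- Scenario 2: k = 0.3127/h, f(k) = 0.1298. Share = (0.0909 - 0.0046)/0.3873 = 0.223; ratio 0.777.

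| | Scenario 1 | Scenario 2 |
|---|---|---|
| Half-life (h) | 3.9 | 2.2 |
| AUC in 0-6 / 6-12 / 12-18 / 18-24 h (units of AUCinf) | 0.699 / 0.895 / 0.964 / 0.442 | 0.777 / 0.964 / 0.994 / 0.264 |
| True AUC24h when the rule reads 48,700 | 48,700/0.699 = about 69,700 | 48,700/0.777 = about 62,700 |
| Cmax at true AUC24h 48,700 | 3,058 | 3,514 |
| Cmax when the rule reads 48,700 | about 4,380 | about 4,520 |

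Both Cmax values in the last row are below 6,100, so the second limit does not compensate.

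**Size at a 4 h half-life** (ka 0.7-6/h assumed): ratio 0.696-0.761. Cmax when the rule reads 48,700 is 3,036/0.696 = about 4,360 to 3,848/0.761 = about 5,060.

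**Size under Table 6** (elimination rate solved so that BID steady-state Cmax/AUC12h equals the Table 6 mean ratio; ka 1-6/h assumed). The ratio runs from 464.1/(1,819/2) = 0.51/h at 30 mg to 2,978/(16,955/2) = 0.35/h at 240 mg. The implied half-life is 0.5-1.6 h. The rule returns 0.998 (30 mg, ka 1.5/h) down to 0.924 (240 mg, ka 6/h), so it is 0.2-7.6% low. Cmax reaches 6,100 at true AUC24h of about 35,000-51,000.

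**Two-compartment variant** (same ratios, with a 4 h terminal phase assumed to carry 10-50% of AUC): 3-13% low. Cmax reaches 6,100 at about 34,000-50,000.

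**TID cover from Table 6.** Scaling the 95th-percentile AUC by 1.5 for a third dose, 48,700/(1.5 x AUC) gives 9.9, 4.7, 2.2, 1.41 and 1.02 from 30 to 240 mg. The tabulated BID Cmax values give 6.8, 3.7, 2.0, 1.34 and 1.01.

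**The case against.** The strongest reply is that the 22-30% shortfall comes from a preclinical projection that the study's own data have overtaken. The MAD predictions in Table 6 are "exposure predictions (based on current study data from the SAD part up to 160mg", and no one-compartment fit to them exists at ka 0.7/h with elimination slower than absorption. With those kinetics the error is small and the Cmax limit usually acts first. Taking whichever limit fires first, the worst one-compartment case passes 48,700 by about 3%. Further guards are the 95th-percentile projection in Section 7.1.1, the 3-fold escalation cap, committee review after each cohort, and a Dose Escalation Committee plan that is not available here. TID is also optional.

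Much of this stands, and it limits the expected consequence. It does not rescue the formula. Table 6 is a BID prediction from preliminary SAD data and does not say whether those data are fasted or fed. MAD dosing is fed only, and slower absorption would enlarge the error. Section 4.4 still argues from a longer half-life: "given the short-estimated half-life of GSK3494245 (approximately 4 h), which enables a short washout period". Section 7.1.1 does not say which daily AUC its power model uses, so the projection may or may not inherit the bias.

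Three smaller points also stand. First, 30% is not a ceiling: an assumed ka of 0.2-0.3/h with a 3-4 h half-life gives about 36%. Second, the downward direction rests on linear PK and equal absorption of the three doses, so one participant's reading could differ, although two assumed saturable-clearance examples also read low, by 33-34%. Third, the mismatch between Section 4.5.3 and the sampling schedule is not specific to TID, because BID is also sampled to 14 h on Day 7.

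**Conclusion.** The concern holds. The TID formula does not fit the TID schedule, nothing elsewhere in the protocol or SAP corrects it, and the error is in the unsafe direction.

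If the drug behaves as in Table 3, neither exposure limit fires until true AUC24h is about 1.3-1.4 times the limit. If it behaves as in Table 6, the shortfall is 0.2-7.6% (3-13% with a slow terminal phase), and the Cmax limit acts at about the same exposure or earlier. These figures assume linear, time-invariant PK, equal absorption of each dose, and the absorption rates stated above. The direction is secure; the size depends on fed-state kinetics that the documents do not give. The formula should be corrected before any TID cohort is dosed. Given the other guards, it is not a reason to stop the study.

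**What to change.** Keep the limit and the action and replace only the TID derivation:

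AUC24h = Day 7 morning AUC(0-6) + Day 6 evening AUC(0-6) + Day 6 evening AUC(0-12).

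The second term stands in for the unsampled afternoon interval and is slightly conservative. The third is closed with the Day 7 pre-dose sample. From the block values above, scenario 1 gives (0.699 + 0.964 + 0.964 + 0.442)/3 = 1.02 and scenario 2 gives (0.777 + 0.994 + 0.994 + 0.264)/3 = 1.01. The one-compartment Table 6 fits give about 1.00. Computed by the linear-up/log-down trapezoid at the scheduled times, the results are 1.019 and 1.004 under Table 3 and 0.97-0.99 under those Table 6 fits.

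A simpler alternative is 3 x AUC6h of the Day 6 evening dose, which gives 96% and 99% under Table 3 and 98-100% under the Table 6 fits.

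Also align the Day 7 sampling windows in Section 4.5.3 with the Schedule of Activities, and state in Section 7.1.1 that the same AUC24h is used wherever daily AUC is modelled for escalation.

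The cost is wording in Section 4.5.3, Section 7.1.1 and the dose-escalation/PK plan, with no new samples. TID AUC margins will look slightly to moderately less favourable.

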4.6. Dose Escalation

As part of this decision-making process, the DEC may decide to escalate or de-escalate the dose in the SAD part and/or the MAD part of the study. The dosing schedule may also be adjusted to add up to two cohorts to further evaluate safety or PK findings at a given dose level, or to evaluate additional dose levels. Two optional cohorts are permitted to allow for assessment in the fasted (after Cohort 2) and fed(after Cohort 3a) states respectively. In the SAD part of the study, additional cohorts will be up to a maximum of two cohorts of 8 participants, investigating up to four dose levels. Addition of extra cohorts may occur if there is greater variability in the PK parameters than expected, or if more dose levels are needed to reach the potentially efficacious exposure. If an additional cohort is required, in either the fasted or fed state, then the nominal illustrative doses in [Table 4](#) and [Table 5](#) may be adjusted. Dosing may also be halted before all planned dose levels have been completed if the stopping criteria has been met, or for any safety concerns, or if review of the data determines that evaluation of further dose levels are not necessary to meet the study objectives.

There will be an open and closed part to the dose escalation meeting. At the beginning of the meeting blinded data will be discussed in an open forum with the Principal Investigator in attendance. If required, the data will then be reviewed in an unblinded fashion by the unblinded members of the DEC. These unblinded members include the CPMS pharmacokineticist and Global Safety representative.

4.6.1. Dose Escalation Committee

The decision to proceed to the next dose level of GSK3494245 in each cohort will be made by a DEC consisting of the Principal Investigator (or appropriate designee), Medical Monitor, GSK Clinical Science Lead and/or Study Team Leader, GSK CPMS pharmacokineticist, a GSK Global Safety representative and GSK Statistician. GSK DEC members will remain blinded throughout the course of the study, **except** for the CPMS pharmacokineticist and Global Safety representative. See also [Table 8](#). Additional

internal GSK safety representatives may be consulted and included in the dose escalation decision making, in a blinded or unblinded manner as deemed necessary by the DEC.

Details of the DEC membership, data to be reviewed and stopping criteria will be outlined in the DEC plan.

4.6.2. Dose Escalation and Safety Review Requirements for SAD part

Dose escalation meeting: The decision to proceed to the next dose level of GSK3494245 and select the dose of GSK3494245 for Cohort 3 will be made at a DEC meeting based on:

- All available safety and tolerability data from a minimum of 48 hrs post-dose from a minimum of 4 or more participants who have received GSK3494245 at the current dose level. Individual safety data (AEs, laboratory safety tests, telemetry, ECGs and vital signs) will be reviewed.
- All available safety and tolerability data accumulated from preceding dose levels and available PK data from current (minimum of 4 or more participants) and preceding dose levels.
- Dose will be escalated by no more than 3-fold of the highest dose level administered in the study and not more than the dose predicted to provide maximum exposure within PK stopping criteria (NOAEL).
- The dose escalation will be halted in case of any tolerability considerations. This will allow careful evaluation of all available data for dose escalation. Based on emerging clinical data, appropriate changes to the dose escalation step-size will be made. The decision to dose escalate will be made by the DEC and will be guided by the safety and SAD PK stopping criteria as outlined in Section 7.1.2 'Dose escalation/stopping criteria'.
- Following completion of Cohort 3, the DEC will review safety, tolerability and PK data from a minimum of 12 evaluable participants in Cohort 3 prior to determining the starting dose for Cohort 3a.

Safety review meeting: The decision to proceed from Cohort 3 Period 1 to subsequent dosing periods will be made by the Principal Investigator and Medical Monitor based on:

- All available safety and tolerability data from a minimum of 48 hrs post-dose from a minimum of 4 or more participants who have received GSK3494245 at the current dose level. Individual safety data (AEs, laboratory safety tests, telemetry, ECGs and vital signs) will be reviewed.

4.6.3. Dose Escalation and Safety Review Requirements for MAD part

A DEC meeting based on all available safety, tolerability and PK data accumulated from the SAD part of the study and the dose modification / stopping criteria will be used to decide:

- The progression to the MAD part

- The starting dose level for Cohort 4 (BID or TID)

The decision for the next repeat dose level (Cohort 5 onwards) will be made at a DEC meeting following completion of a minimum 7 days dosing in no fewer than 4 participants who have received GSK3494245 from the previous repeat dose cohort and will be based on:

- Assessment of safety, plasma GSK3494245 PK concentrations obtained from a minimum of 4 participants from the previous repeat dose cohort. Individual safety data (AEs, laboratory safety tests, telemetry, ECGs and vital signs) will be reviewed.
- Evaluation of all available safety, tolerability and PK data accumulated from the previous repeat dose cohort.
- Doses will be escalated by no more than 3-fold and up to a dose predicted to provide maximum exposure within PK stopping criteria
- The dose escalation will be halted in case of any tolerability considerations. This will allow careful evaluation of all available data for dose escalation. Based on emerging clinical data, appropriate changes to the dose escalation step-size will be made. The decision to dose escalate will be made by the DEC and will be guided by the safety and MAD PK stopping criteria as outlined in Section 7.1.2 'Dose escalation/stopping criteria'.

- **CCI**

